5.1.3 Subject Exclusion Criteria

The subject must be excluded from participating in the trial if the subject:

1. Is currently participating and receiving study therapy or has participated in a study of an investigational agent and received study therapy or used an investigational device within 4 weeks of the first dose of treatment.
2. Has a diagnosis of immunodeficiency or is receiving systemic steroid therapy or any other form of immunosuppressive therapy within 7 days prior to the first dose of trial treatment.

3. Has a known history of active TB (Bacillus Tuberculosis)
4. Hypersensitivity to pembrolizumab or any of its excipients.
5. Has had a prior anti-cancer monoclonal antibody (mAb) within 4 weeks prior to study Day 1 or who has not recovered (i.e., \leq Grade 1 or at baseline) from adverse events due to agents administered more than 4 weeks earlier.
6. Has had prior chemotherapy, targeted small molecule therapy, or radiation therapy within 2 weeks prior to study Day 1 or who has not recovered (i.e., \leq Grade 1 or at baseline) from adverse events due to a previously administered agent.
 - Note: Subjects with \leq Grade 2 neuropathy are an exception to this criterion and may qualify for the study.
 - Note: If subject received major surgery, they must have recovered adequately from the toxicity and/or complications from the intervention prior to starting therapy.
7. Has a known additional malignancy that is progressing or requires active treatment. Exceptions include basal cell carcinoma of the skin or squamous cell carcinoma of the skin that has undergone potentially curative therapy or in situ cervical cancer.
8. Has known active central nervous system (CNS) metastases and/or carcinomatous meningitis. Subjects with previously treated brain metastases may participate provided they are stable (without evidence of progression by imaging for at least four weeks prior to the first dose of trial treatment and any neurologic symptoms have returned to baseline), have no evidence of new or enlarging brain metastases, and are not using steroids for at least 7 days prior to trial treatment. This exception does not include carcinomatous meningitis which is excluded regardless of clinical stability.
9. Has active autoimmune disease that has required systemic treatment in the past 2 years (i.e. with use of disease modifying agents, corticosteroids or immunosuppressive drugs). Replacement therapy (eg., thyroxine, insulin, or physiologic corticosteroid replacement therapy for adrenal or pituitary insufficiency, etc.) is not considered a form of systemic treatment.
10. Has known history of, or any evidence of active, non-infectious pneumonitis.
11. Has an active infection requiring systemic therapy.
12. Has a history or current evidence of any condition, therapy, or laboratory abnormality that might confound the results of the trial, interfere with the subject's participation

- for the full duration of the trial, or is not in the best interest of the subject to participate, in the opinion of the treating investigator.
13. Has known psychiatric or substance abuse disorders that would interfere with cooperation with the requirements of the trial.
 14. Is pregnant or breastfeeding, or expecting to conceive or father children within the projected duration of the trial, starting with the screening visit through 120 days after the last dose of trial treatment.
 15. Has received prior therapy with an anti-PD-1, anti-PD-L1, or anti-PD-L2 agent.
 16. Has a known history of Human Immunodeficiency Virus (HIV) (HIV 1/2 antibodies).
 17. Has known active Hepatitis B (e.g., HBsAg reactive) or Hepatitis C (e.g., HCV RNA [qualitative] is detected), or other active viral hepatitis. Patients with treated and resolved hepatitis B or C are eligible. Patients with active liver disease, except liver abnormalities directly attributable to lymphoma are ineligible,
 18. Has received a live vaccine within 30 days of planned start of study therapy.

Note: Seasonal influenza vaccines for injection are generally inactivated flu vaccines and are allowed; however intranasal influenza vaccines (e.g., Flu-Mist®) are live attenuated vaccines, and are not allowed.

5.2 Patient Recruitment and Registration

Patients will be recruited from the Investigators' clinical practices at the Perlmutter Cancer Center (PCC) at NYU Langone Health, Winship Cancer Institute of Emory University, Massachusetts General Hospital (MGH) and Beth Israel Deaconess Medical Center of MGH in Boston, MA. Prior to study entry, a patient's eligibility must be approved in writing by the NYU Clinical Trials Office.

Target accrual for this study is 26-29 patients. Prospective subjects will receive detailed information regarding this study; its investigational nature, required study procedures, alternative treatments, risks and potential benefits of the study. All questions will be answered by the PI and/or qualified research personnel.

The Principal Investigator will:

1. Obtain signed and dated informed consent from the potential subject before any study specific procedures are performed.

2. Determine patient eligibility. (See Section 5.1.2 and 5.1.3)
3. Submit registration to NYU Langone Health Perlmutter Cancer Center Clinical Trials Office (CTO)
4. Receive registration confirmation from the designated CTO staff member at NYU Perlmutter Cancer Center CTO, including a unique study identification number assigned to the patient, which will be distributed to the study team upon registration of the patient.

Enrollment in the study requires that all inclusion and exclusion criteria have been met. Enrollment occurs upon confirmation of registration from the NYU Langone Health Perlmutter Cancer Center (PCC) Clinical Trials Office (CTO). The following materials must be submitted to the research coordinator for registration:

1. Complete signed and dated informed consent form
2. Complete signed and dated eligibility checklist
3. All supporting documentation verifying each criterion has been met

Registration will occur within 48 hours of research coordinator receipt of all of the above documents. A written confirmation of enrollment including a unique study identification number assigned by the research coordinator will be disbursed to the study team upon registration. The patient will not be identified by name. This is the point, at which, the patient is considered accrued on study.

5.2.1 Informed Consent

Investigators will stress that participation in the study is completely voluntary, he/she may withdraw from the study at any time and it will not affect the care patients receive or result in any loss of benefits to which patients are otherwise entitled.

For non-English speaking patients, institutional translation services will be utilized. All procedures for consenting non-English speaking patients will be in accordance with NYU PCC CTO guidelines and policies.

For patients who cannot read; a witness, not related to the research study will be present. The consent will be read to the patient. The patient will also be allowed to ask any questions s/he may have. The investigator will ask the patient questions to ensure s/he understands the study. If the investigator determines the subject understands the study, the patient will mark an X where his/her name would go and the witness will sign the consent form.

5.2.2 Documentation of Consent

The Primary Investigator or IRB approved sub-investigator will be responsible for documentation in the medical record that consent has been obtained from all participants. A signed copy of the consent form will be given to each participant. Original consent forms will be stored in the subject's medical chart.

5.2.3 Multi-Site Surveillance

As the lead investigator in this multi-site trial, the Overall Primary Investigator is responsible for organizing and conducting bi-weekly teleconferences with all participating sites. The PI will also be responsible for including data from all of the participating sites within the overall trial's quarterly Data and Safety Monitoring report to the DSMC to include minutes from bi-weekly PI teleconferences. Each participating site will be responsible for submitting the results and recommendations from the DSMC's quarterly reviews to their IRB of record at the time of continuing review. Additionally, the NYU Langone Health PCC Clinical Trial Office, Quality Assurance Unit will provide extensive monitoring remotely, to ensure completeness and compliance with the protocol, in addition to consistency of the data.

5.2.4 Patient Informed Consent at Additional Sites

The Principal Investigator (PI) at each participating site will identify the physician members of the study team who will be obtaining consent and signing the consent form for this clinical trial. It is NYU Langone Health's policy that Nurses and Fellows cannot obtain consent to greater than minimal risk trials, unless Fellows are listed as Co-Investigators.

The Investigator must ensure that each participant, or his/her legally acceptable representative, is fully informed about the nature and objectives of the study and possible risks associated with participation. All participants must be provided a consent form describing this study and providing sufficient information for participants to make an informed decision about their participation in this study. The formal consent of a participant, using the IRB approved consent form, must be obtained before the participant is involved in any study-related procedures. The consent form must be signed and dated by the participant or the participant's legally authorized representative (if applicable), and by the person obtaining consent. The participant must be given a copy of the signed and dated consent document. The original signed copy of the consent document must be retained in the medical record or research file.

All parties will ensure protection of participant personal data and will not include participant names on any sponsor forms, reports, publications, or in any other disclosures, except where required by laws. In case of data transfer, NYU Langone Health Perlmutter Cancer Center (PCC) will maintain high standards of confidentiality and protection of participant personal data.

The informed consent form must be in compliance with ICH/GCP, local regulatory requirements, and legal requirements. The informed consent form used in this study, and any changes made during the course of the study, must be prospectively approved by both the IRB and NYU Langone Health before use.

5.2.5 Patient Registration at Additional Sites

Enrollment at additional sites can occur once each site's IRB has approved this protocol, a copy of each site's IRB approval, Citi training certificates, Medical Licenses and signed CVs are provided to NYU Langone Health Perlmutter Cancer Center Clinical Trials Office. Once, all required documents are provided to the NYU Langone Health PCC Clinical Trials Office and activation notification will be sent to the PI and research coordinator of the participating site.

Central registration for this study will take place at NYU Langone Health PCC Quality Assurance Unit ([contact]).

Each patient must sign and date an informed consent form before undergoing any study specific procedures unless a procedure is being performed as part of the patient's standard of care. Once a patient has signed consent, each site must notify the NYU Langone Health PCC Quality Assurance Unit and forward a copy of the signed consent with all supporting documentation to NYU Langone Health PCC Clinical Trials Office within 24 hours.

Enrollment in the study requires that all inclusion and exclusion criteria have been met. Enrollment occurs upon confirmation of registration from the NYU Langone Health PCC Clinical Trials Office. The following materials must be submitted to the Quality Assurance Unit at NYU Langone Health via email ([contact]):

1. Complete signed and dated informed consent form
2. Complete signed and dated informed consent checklist
3. Complete signed and dated eligibility checklist
4. All supporting documentation verifying each criterion has been met.

Registration will occur once the Senior Research Nurse for the Quality Assurance Unit conducts a central review of the submitted materials. Once eligibility is verified, a unique subject study number will be issued within 48 hours of receiving all required registration material. This number is unique to the participant and must be written on all data and correspondence for the participant. The NYU Langone Health PCC CTO will return a signed eligibility confirmation worksheet email with the subject's unique study number.

The subject will not be identified by name. This is the point, at which, the subject is considered accrued on study. Protocol treatment should begin within designated timeframe; issues that would cause treatment delays should be discussed with the overall PI, [name].

All screen failures/ineligible subjects, as well as subject's who withdraw consent prior to initiation of protocol therapy must be submitted to the CTO in a manner analogous to the procedures noted above. Applicable source documentation will be required within the corresponding submissions.

Each site is responsible for reporting all unexpected problems involving risks to participants or others to the NYU Langone Health PCC Clinical Trials Office and to their IRB as per site institutional policy.

5.3 Trial Treatments

The treatment to be used in this trial is outlined below in **Table 2**

Table 2 Trial Treatment

Drug	Dose/Potency	Dose Frequency	Route of Administration	Regimen/ Treatment Period	Use
Pembrolizumab	200 mg	Q3W	IV infusion	Day 1 of each 3 week cycle	Experimental
Lenalidomide	10mg-20mg	Daily for 14 days every 21 days	PO	Day 1-14 of 21	Experimental

5.3.1 Dose Selection/Modification/ Dose Limiting Toxicity

5.3.1.1 Dose Selection

The rationale for selection of doses to be used in this trial is provided in Section 4.0 – Background and Rationale.

Details on preparation and administration of pembrolizumab (MK-3475) are provided in the package insert.

5.3.1.2 Dose Modification

5.2.1.2.1 Pembrolizumab

Adverse events (both non-serious and serious) associated with pembrolizumab exposure may represent an immunologic etiology. These adverse events may occur shortly after the first dose or several months after the last dose of treatment. Pembrolizumab must be withheld for drug-related toxicities and severe or life-threatening AEs as per Table 3 below. See Section 5.6.1 and Events of Clinical Interest Guidance Document for supportive care guidelines, including use of corticosteroids.

Table 3

Dose Modification Guidelines for Drug-Related Adverse Events

Toxicity	Hold Treatment For Grade	Timing for Restarting Treatment	Discontinue Subject
Diarrhea/Colitis	2-3	Toxicity resolves to Grade 0-1.	Toxicity does not resolve within 12 weeks of last dose or inability to reduce corticosteroid to 10 mg or less of prednisone or equivalent per day within 12 weeks.
	4	Permanently discontinue	Permanently discontinue
AST, ALT, or Increased Bilirubin	2	Toxicity resolves to Grade 0-1	Toxicity does not resolve within 12 weeks of last dose.
	3-4	Permanently discontinue (see exception below) ₁	Permanently discontinue
Type 1 diabetes mellitus (if new onset) or Hyperglycemia	T1DM or 3-4	Hold pembrolizumab for new onset Type 1 diabetes mellitus or Grade 3-4 hyperglycemia associated with evidence of beta cell failure.	Resume pembrolizumab when patients are clinically and metabolically stable.
Hypophysitis	2-3	Toxicity resolves to Grade 0-1	Toxicity does not resolve within 12 weeks of last dose or inability to reduce corticosteroid to 10 mg or less of prednisone or equivalent per day within 12 weeks.
	4	Permanently discontinue	Permanently discontinue
Hyperthyroidism	3	Toxicity resolves to Grade 0-1	Toxicity does not resolve within 12 weeks of last dose or inability to reduce corticosteroid to 10 mg or less of prednisone or equivalent per day within 12 weeks.

Toxicity	Hold Treatment For Grade	Timing for Restarting Treatment	Discontinue Subject
	4	Permanently discontinue	Permanently discontinue
Hypothyroidism	2-4	Therapy with pembrolizumab can be continued while treatment for the thyroid disorder is instituted	Therapy with pembrolizumab can be continued while treatment for the thyroid disorder is instituted.
Infusion Reaction	3-4	Permanently discontinue	Permanently discontinue
Pneumonitis	2	Toxicity resolves to Grade 0-1	Toxicity does not resolve within 12 weeks of last dose or inability to reduce corticosteroid to 10 mg or less of prednisone or equivalent per day within 12 weeks.
	3-4	Permanently discontinue	Permanently discontinue
Renal Failure or Nephritis	2	Toxicity resolves to Grade 0-1	Toxicity does not resolve within 12 weeks of last dose or inability to reduce corticosteroid to 10 mg or less of prednisone or equivalent per day within 12 weeks.
	3-4	Permanently discontinue	Permanently discontinue
All Other Drug-Related Toxicity ²	3 or Severe	Toxicity resolves to Grade 0-1	Toxicity does not resolve within 12 weeks of last dose or inability to reduce corticosteroid to 10 mg or less of prednisone or equivalent per day within 12 weeks.
	4	Permanently discontinue	Permanently discontinue

Note: Permanently discontinue for any severe or Grade 3 drug-related AE that recurs or any life-threatening event.
 
¹ For patients with liver metastasis who begin treatment with Grade 2 AST or ALT, if AST or ALT increases by greater than or equal to 50% relative to baseline and lasts for at least 1 week then patients should be discontinued.
 
² Patients with intolerable or persistent Grade 2 drug-related AE may hold study medication at physician discretion. Permanently discontinue study drug for persistent Grade 2 adverse reactions for which treatment with study drug has been held, that do not recover to Grade 0-1 within 12 weeks of the last dose.
			

Dosing interruptions are permitted in the case of medical / surgical events or logistical reasons not related to study therapy (e.g., elective surgery, unrelated medical events, patient vacation, and/or holidays). Subjects should be placed back on study therapy within 3 weeks of the scheduled interruption, unless otherwise discussed with the Sponsor. The reason for interruption should be documented in the patient's study record.

5.2.1.2.2 Lenalidomide

Adverse events (both non-serious and serious) associated with lenalidomide exposure may represent an immunologic etiology. These adverse events may occur shortly after the first dose or several months after the last dose of treatment. Lenalidomide must be withheld for drug-related toxicities and severe or life-threatening AEs as per Table 3 below

Table 4
Dose Modification Guidelines for Drug-Related Adverse Events

Toxicity	Hold Treatment For Grade	Timing for Restarting Treatment	Discontinue Subject
Neutropenia and thrombocytopenia	4	Toxicity resolves to Grade 1-2	Toxicity does not resolve within 1 month of last dose
Venous thrombosis/ Embolism	3-4	At investigator discretion after starting anticoagulation	At investigator discretion
Skin rash	4	n/a	Permanently discontinue
	2-3	Resume when rash resolves to less or equal grad 1	Toxicity does not resolve within 1 month of last dose
Neuropathy	3	Toxicity resolves to Grade 0-1	Toxicity does not resolve within 1 month
	4	Permanently discontinue	Permanently discontinue
Hypothyroidism	2-4	Therapy with can be continued while treatment for the thyroid disorder is instituted	Therapy with can be continued while treatment for the thyroid disorder is instituted.
Allergic reaction	3-4	Permanently discontinue	Permanently discontinue
Constipation	3-4	Toxicity resolves to Grade 1-2	Toxicity does not resolve within 1month
Cardiac arrhythmias	2	Toxicity resolves to Grade 0-1	Toxicity does not resolve within 1 month.
	3-4	Permanently discontinue	Permanently discontinue

Toxicity	Hold Treatment For Grade	Timing for Restarting Treatment	Discontinue Subject
Other non hematological Drug-Related Toxicity	3 or Severe	Toxicity resolves to Grade 0-1	Toxicity does not resolve within 1 month.
	4	Permanently discontinue	Permanently discontinue
Note: Permanently discontinue for any severe or Grade 3 drug-related AE that recurs or any life-threatening event.			

5.3.1.3 Definition of Dose-Limiting Toxicity

Toxicities should be attributable to the study intervention to constitute a dose limiting toxicity (DLT). Toxicity will be graded using the Common Toxicity Criteria for Adverse Events (CTCAE) version 4.0. A DLT is defined by the occurrence of any of the following toxicities (CTCAE v.4.03) for up to 21 days from initiation of the combination therapy (i.e. within the first cycle of therapy) in order to evaluate the potential toxicities of these therapies.

Non-Hematological dose-limiting toxicity

Any Grade 3 or Grade 4 non-hematological toxicity that is possibly, probably or definitely attributable to the regimen pembrolizumab-lenalidomide is considered a DLT, including the following:

- Any type of grade 3-4 hypersensitivity reaction (i.e.: allergic reaction, anaphylaxis, serum sickness, skin disorders, etc.), regardless of attribution.
- Any type of grade 3-4 immune related adverse event
- Inability to receive pembrolizumab-lenalidomide therapy within a 1 month period of scheduled treatment, due to a therapy related event.
- Grade 3 nausea/vomiting/diarrhea lasting longer than 24hours despite maximal care or Grade 4 nausea/vomiting/diarrhea

Any other non-hematologic clinical toxicity considered at least possibly related to treatment defined as any Grade 3 or greater with the specific exception of:

- Grade 3 dehydration that, in the opinion of the investigator, occurs in the setting of inadequate prophylactic measures or compliance with supportive care measures and lasts for less than 48 hours
- Grade 3 fatigue or Grade 4 fatigue that lasts for ≤ 5 days
- Grade 3 fever
- Grade 3 ALT/AST elevation for which total bilirubin remains within normal limits.

Hematologic dose-limiting toxicity

The following hematological toxicity possibly, probably or definitely attributable to the regimen of pembrolizumab and lenalidomide is considered a DLT. Growth factors are allowed per treating investigator's discretion in patients at high risk for febrile neutropenia.

- Grade 4 neutropenia associated with fever (> 38.5) of any duration
- Grade 3 neutropenia associated with fever (> 38.5) of any duration
- Grade 4 thrombocytopenia or Grade 3 thrombocytopenia with bleeding or any requirement for platelet transfusion.
- Grade 4 anemia unexplained by underlying disease
- Myelosuppression that causes a delay of > 7 days in next cycle of pembrolizumab/lenalidomide

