6.3.2 Evaluating Adverse Events

An investigator who is a qualified physician will evaluate all adverse events according to the NCI Common Terminology for Adverse Events (CTCAE), version 4.0. Any adverse event which changes CTCAE grade over the course of a given episode will have each change of grade recorded on the adverse event case report forms/worksheets.

All adverse events regardless of CTCAE grade must also be evaluated for seriousness.

Table 7 Evaluating Adverse Events

An investigator who is a qualified physician, will evaluate all adverse events as to:

V4.0 CTCAE Grading	Grade 1	Mild; asymptomatic or mild symptoms; clinical or diagnostic observations only; intervention not indicated.
	Grade 2	Moderate; minimal, local or noninvasive intervention indicated; limiting age-appropriate instrumental ADL.
	Grade 3	Severe or medically significant but not immediately life-threatening; hospitalization or prolongation of hospitalization indicated; disabling; limiting self-care ADL.
	Grade 4	Life threatening consequences; urgent intervention indicated.
	Grade 5	Death related to AE
Seriousness	A serious adverse event is any adverse event occurring at any dose or during any use of Merck product that:	
	† Results in death ; or	
	† Is life threatening ; or places the subject, in the view of the investigator, at immediate risk of death from the event as it occurred (Note: This does not include an adverse event that, had it occurred in a more severe form, might have caused death.); or	
	† Results in a persistent or significant disability/incapacity (substantial disruption of one’s ability to conduct normal life functions); or	
	† Results in or prolongs an existing inpatient hospitalization (hospitalization is defined as an inpatient admission, regardless of length of stay, even if the hospitalization is a precautionary measure for continued observation. (Note: Hospitalization [including hospitalization for an elective procedure] for a preexisting condition which has not worsened does not constitute a serious adverse event.); or	
	† Is a congenital anomaly/birth defect (in offspring of subject taking the product regardless of time to diagnosis); or	
	Is a new cancer ; (that is not a condition of the study) or	

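### The lenalidomide hold rule cites the wrong table and, as tabulated in Table 4, is less protective than the DLT list for two complicated Grade 3 cytopenias

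*Combined protocol and SAP*

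**What the plan says.** The hematologic part of the DLT list in Section 5.3.1.3 includes "Grade 3 neutropenia associated with fever (> 38.5) of any duration" and "Grade 4 thrombocytopenia or Grade 3 thrombocytopenia with bleeding or any requirement for platelet transfusion", when at least possibly attributable to the regimen. It also includes Grade 4 neutropenia with fever and Grade 4 anemia not explained by the underlying disease.

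The lenalidomide rules are in the subsection printed as 5.2.1.2.2, within Section 5.3.1.2. They open with "Lenalidomide must be withheld for drug-related toxicities and severe or life-threatening AEs as per Table 3 below". The table that follows is Table 4; Table 3 is the pembrolizumab table in the preceding subsection.

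Three parts of Table 4 bear on cytopenias:

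- The row "Neutropenia and thrombocytopenia" holds at Grade 4 only. It allows restart at Grade 1-2 and discontinues if there is no recovery within 1 month of the last dose.
- The row "Other non hematological Drug-Related Toxicity" holds at Grade 3 or severe.
- The note reads "Permanently discontinue for any severe or Grade 3 drug-related AE that recurs or any life-threatening event".

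Table 3 has a wider catch-all, "All Other Drug-Related Toxicity". It holds at Grade 3 or severe and stops treatment permanently at Grade 4, with no restriction to non-hematological events.

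**The concern.** A DLT list and a hold table serve different purposes and need not match. It is odd, though, for the hold threshold to be the weaker of the two for an event that the protocol itself calls dose-limiting. Table 4 interrupts lenalidomide for Grade 2 rash, Grade 2 arrhythmia and Grade 3 constipation, but has no entry for a first Grade 3 neutropenia with fever. If drug-related, the same event requires a pembrolizumab hold under Table 3. Yet the lenalidomide background (Section 4.1.3) names the blood and lymphatic systems among the usual sites of that drug's adverse events.

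The toxicity is foreseeable. The same background reports DLTs in 3 of 13 patients at lenalidomide 25 mg in the myeloma study of this pair with dexamethasone, and Grade 3 and Grade 4 neutropenia are among them.

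What is at stake is patient safety and consistency between sites. Lenalidomide is taken daily by outpatients at several centers. DLTs are counted only in cycle 1, but Table 4 governs holds throughout treatment, including Phase 2. A site following Table 4 exactly, and a site following the sentence above it literally, would act differently on the same event.

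**Working it through.** **Step 1: set the rules side by side.** The last column applies Table 3 to lenalidomide, as the introducing sentence literally directs, for drug-related events.

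| Event | DLT in 5.3.1.3 (cycle 1) | Table 4 | Table 3, read literally |
|---|---|---|---|
| First Grade 3 neutropenia with fever >38.5 | Yes | No required hold | Hold |
| First Grade 3 thrombocytopenia with bleeding or transfusion | Yes | No required hold | Hold |
| Grade 4 neutropenia with fever | Yes | Hold, restart at Grade 1-2 | Permanent stop |
| Grade 4 thrombocytopenia | Yes | Hold, restart at Grade 1-2 | Permanent stop |
| Grade 4 anemia unexplained by disease | Yes | No row; only the note's life-threatening limb | Permanent stop |

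The two tables disagree in every row, with one possible exception: Grade 4 anemia, if it is judged life-threatening. In the DLT list, platelet transfusion may be tied to Grade 3 thrombocytopenia or may stand alone; the result is the same on either reading.

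**Step 2: look for another route to a hold within Table 4.**

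- Catch-all row: this applies only if the accompanying fever or bleed is itself a Grade 3 or severe drug-related non-hematological event. Lower-grade bleeding, or transfusion alone, does not meet it.
- Recurrence limb of the note: this does not reach a first event.
- Life-threatening limb of the note: Table 7 (Section 6.3.2, Evaluating Adverse Events) describes Grade 3 as short of an immediate threat to life. It treats an event as life threatening when it "places the subject, in the view of the investigator, at immediate risk of death from the event as it occurred". The limb therefore depends on judgement. If Grade 4 alone triggered it, the note would also contradict the cytopenia row, which lets Grade 4 patients restart.

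**Step 3: look for a rule elsewhere.**

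- Section 5.7 requires discontinuation for unacceptable adverse experiences, but refers back to the dose-modification section.
- Section 6.2.3 requires laboratory results to be reviewed and judged acceptable before each dose of trial treatment, but gives no count limit. The flow chart schedules cycle 1 blood counts on days 1, 8 and 15, not daily.
- Section 8.1 provides bi-weekly calls, with no count limit.
- No section says that a patient with a DLT must hold or stop lenalidomide.

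**Step 4: doses at issue.** Lenalidomide is given on days 1-14 (Section 5.3, Table 2). For an event found on day d, up to day 14:

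- doses remaining = 15 − d if that day's dose is not yet taken;
- doses remaining = 14 − d if it is.

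| Day found | Doses left | Share of 14 | At 15 mg | At 20 mg |
|---|---|---|---|---|
| 2 | 13 or 12 | 93% or 86% | 195 or 180 mg | 260 or 240 mg |
| 8 | 7 or 6 | 50% or 43% | 105 or 90 mg | 140 or 120 mg |
| 14 | 1 or 0 | 7% or 0% | 15 or 0 mg | 20 or 0 mg |
| 15 | 0 | 0% | 0 mg | 0 mg |

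Over days 2-14 the range is 0 to 13 doses. Day 8 is used because a count is scheduled then in cycle 1. It is neither a bound nor an expected day, since Section 6.2 allows unscheduled assessments.

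**The case against.** The strongest objection is that the protocol, read as written, does require a hold. The operative sentence points to Table 3, and Table 3 holds at Grade 3 without excluding hematological events. This stands in part. A reader might infer that nothing in the protocol requires lenalidomide to be held for these events; the documents do not support so flat a statement. But the sentence sits under the lenalidomide heading, nearly repeats the pembrolizumab sentence, and comes directly before Table 4, so a numbering slip is much the likelier explanation. It also means that correcting the table number alone would remove the only wording that now requires the hold.

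A second objection is that other controls suffice. The laboratory review before dosing is mandatory, the DLT list contemplates count-related cycle delays, and a site holding pembrolizumab for such an event is unlikely to continue lenalidomide. These make continued dosing less likely. They set no threshold and do not close the gap between visits.

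Third, the myeloma evidence is limited. That study used 25 mg plus dexamethasone, whereas this trial stops at 20 mg. All its patients recovered from their DLTs without discontinuing treatment, though that does not exclude temporary holds. The report does not say whether the neutropenia was febrile. It shows that neutropenia is foreseeable, and no more.

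Finally, the dose range follows mechanically from the day number and says nothing about frequency or harm. That is correct, and neither is claimed.

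**Conclusion.** The lenalidomide hold rule is internally inconsistent and, on its more likely reading, less protective than the DLT list for two first events: Grade 3 neutropenia with fever >38.5, and Grade 3 thrombocytopenia with bleeding or platelet transfusion. The exceptions are those in Step 2. Grade 4 anemia is a related loose end, covered only if judged life-threatening.

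The conclusion assumes that the Table 3 citation is a slip. If it is not, the defect becomes a direct conflict between two tables, and it still needs correcting.

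A reader might infer that the gap distorts dose finding. It does not: these events count as DLTs whatever Table 4 says, so DLT counts, the MTD rule, power and alpha are unchanged. A reader might also infer that patients will often be dosed through such events. The documents give no rate, and investigators remain free to hold on judgement. This is a safety clarification that should be made at the next amendment. Confidence is medium.

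**What to change.** Make both edits together:

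1. In the sentence introducing Table 4, cite Table 4 instead of Table 3.
2. Extend Table 4's cytopenia row to hold lenalidomide for Grade 4, for Grade 3 neutropenia with fever >38.5, and for Grade 3 thrombocytopenia with bleeding or platelet transfusion. Restart when the count is back to Grade 1-2, or to baseline for patients enrolled with low counts from marrow involvement, and the fever or bleeding has resolved. Keep the 1-month limit.

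The baseline clause is needed because Table 1 admits patients with marrow involvement at an ANC of 800 or more. The documents do not give the grade cut-points. If Grade 3 neutropenia begins just below 1,000 (an assumption), patients entering at 800-999 start at Grade 3 and might never reach Grade 1-2. If it begins at 800 or lower, no one is affected.

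These edits leave Grade 4 anemia to the note; the sponsor should confirm that this is intended.

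The cost is one table row and one table number in an amendment, with no extra patients, visits or tests. The downsides are occasional extra interruptions (6 or 7 of 14 doses for an event found on day 8) and the 1-month discontinuation limit, which would newly apply to these Grade 3 events. Uncomplicated Grade 3 counts would still need no hold.
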